#### **4.2.1 PK results**

Measurements of plasma PK concentrations that are below the limit of quantification (BLQ) will be imputed with half of the lower limit of quantification (LLOQ) for the purpose of calculating the geometric mean and its 95% CI, the geometric CV, the arithmetic mean and SD for summaries and figures. Descriptive statistics of concentrations will be calculated if at least 2/3rd of the individual data points are quantifiable ( $\geq LLOQ$ ).

The following rules will apply for the summaries, listings and figures:

- If no participants have data, only “n=0” will be presented. The other descriptive statistics will be left blank.
- Descriptive statistics of plasma concentrations will be calculated if at most 1/3rd of the individual data points are missing or are not quantifiable (<LLOQ) at the given time-point. Values that are BLQ will be replaced by the numerical value of the LLOQ/2 in this instance. However, if n<3, then only n, minimum and maximum will be presented, and the median will also be presented if n=3. The other descriptive statistics will be left blank.
- For the calculation of plasma PK parameters, all BLQ values occurring prior to Cmax will be replaced by “0”, except for embedded BLQ values (between two measurable data points) which will be treated as missing. Post-Cmax BLQ values will be treated as missing. The Pharmacokinetic analysis will be performed in accordance to the User guide for Clinical Pharmacokinetics Modeling and Simulation version8 issued by UCB.
- The geometric CV will be calculated using the following formula where SD is the standard deviation from the log-transformed data:  
$$\text{Geometric CV (\%)} = \text{sqrt}[(\exp (SD^2) - 1)] \times 100$$
- The 95% CI for the geometric mean should be left blank if the SD is 0.
- For the individual figures, any concentrations that are BLQ will be regarded as missing, with the exception of predose BLQ measurements on Day 1 and Day 10, which will be imputed with zero for linear scale plots.
- Values below the LLOQ will be reported as BLQ in the listings.

#### **4.2.2 Safety laboratory data**

The rules for handling values that are BLQ in the safety laboratory data will be the same as those described for PK data in Section 4.2.1.

#### **4.2.3 ECG data**

For the 12-lead ECG data, all calculations of changes from Baseline and descriptive statistics will be based on the mean of the triplicate assessments at each timepoint. In the event that there are not 3 available measurements at a given timepoint, the mean will be calculated based on the number of measurements for which data are provided.

#### **4.2.4 Incomplete dates and times**

Partial dates may be imputed for the following reasons:

- Classification of AEs as treatment-emergent
- Classification of medications as prior or concomitant

Imputed dates will not be shown in the listings; all dates will be displayed as reported in the database.

##### Partial start date

The following rules will be applied for partial start dates:

- If only the month and year are specified and the month and year of the first dose of study medication is not the same as the month and year of the start date, then use the 1st of the month, or the date of Screening if this is later (if the latter imputation results in an end date that is earlier than the start date, then use the 1st of the month). If time is missing this will be imputed as 00:00 h
- If only the month and year are specified and the month and year of the first dose of study medication is the same as the month and year of the start date, then use the date of the first dose of study medication. If this results in an imputed start date that is after the specified end date, then use the 1st of the month, or the date of Screening if this is later (if the latter imputation results in an end date that is earlier than the start date, then use the 1st of the month). If the imputed date is the date of dosing then time will be imputed as the start time of the dosing (ie, event will be regarded as treatment-emergent)
- If only the year is specified, and the year of the first dose of study medication is not the same as the year of the start date then use January 01 will be used. If time is missing this will be imputed as 00:00 h
- If only the year is specified, and the year of the first dose of study medication is the same as the year of the start date, then the date of the first dose of study medication will be used. If this results in an imputed start date that is after the specified end date, then January 01, or the date of screening if this is later will be used (if the latter imputation results in an end date that is earlier than the start date, then January 01 will be used). If the imputed date is the date of first dose of study medication then time will be imputed as the start time of the study medication intake (ie, event will be regarded as treatment-emergent)
- If the start date is completely unknown, then use the date of dosing. If this results in an imputed start date that is after the specified end date, then use January 01 of the year of the end date, or the date of Screening if this is later.

#### Missing start time

Missing start times will be imputed as 00:00h or with the time of dosing for events occurring on the date of administration of PSL.

#### Partial stop date

The following rules will be applied for partial stop dates:

- If only the month and year are specified, then use the last day of the month
- If only the year is specified, then use December 31 of the known year
- If the stop date is completely unknown, do not impute the stop date

#### Calculation of duration of each AE when there being missing or partially missing date and/or time

Missing or partially missing dates and/or times will be imputed as described in Section 4.2.4. AE duration is computed and reported in day and time format: xx d hh:mm. Duration is not calculated when the outcome date is missing.

**Table 4-1: Calculation rules for duration of adverse events**

Data availability	Onset date/time	Outcome date/time	Calculation rules
Complete data	D1/T1	D2/T2	Duration = $[(D2 - D1) * 24 + (T2 - T1)] / 24$ d
End time missing	D1/T1	D2/--	End time is substituted by time 23:59h (=23.98 in decimal format) Duration = $<[(D2 - D1) * 24 + (23.98 - T1)] / 24$ d
Start time missing	D1/--	D2/T2	Onset time is substituted by time 00:00h Duration = $<[(D2 - D1) * 24 + T2] / 24$ d
Start and end time missing	D1/--	D2/--	Duration = $<D2 - D1 + 1$
Start day and time missing	--/--	D2/T2	Duration = $[(D2 - D0) * 24 + (T2 - T0)] / 24$ d For a participant in the FAS, D0 and T0 are the date and time of first administration of study medication and for screen failures, D0 is the date of the screening visit and T0 = 00:00h
End day and time missing	D1/T1	--/--	If the stop date is missing, duration will not be calculated.
Start and end date missing	--/--	--/--	If the stop date is missing, duration will not be calculated.

FAS=full analysis set.

#### 4.3 Handling of repeated and unscheduled measurements

All repeated and unscheduled measurements will be presented in the data listings, where applicable. The following general rules will apply to all repeated and unscheduled measurements:

- For repeated measurements obtained prior to the first dose of study medication the latest value (which may be scheduled or unscheduled) will be used in the calculation of the descriptive statistics
- For repeated measurements obtained at the designated Baseline visit, the latest value (which may be scheduled or unscheduled) will be defined as the Baseline provided that this occurred prior to the first dose of study medication
- Unscheduled and repeated measurements will not be used in the descriptive statistics at time points after first dose of study medication
- Unscheduled measurements performed for the Early Withdrawal (EW) visit will be assigned to the EOS visit (Section 4.4) and analyzed accordingly as an EOS visit.

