c On dosing days, vital signs will be performed predose and 3 hours postdose. Blood pressure measurements will be performed in both supine and standing positions for orthostatic measurement at Screening (supine BP after the study participant has been lying down for 5 minutes and then standing BP after 1 minute and 3 minutes) and in a supine position for routine BP measurements at all assessments.

d 12-lead ECG will be performed after a rest of  $\geq 5$  minutes at Screening and at predose, 24 hours postdose, and at the SFU Visit. All ECG recordings will be performed in triplicate but no more than 2 to 3 minutes apart.

e PSL 200mg will be administered in the morning on Day 1 during the Single-dose Period.

f PSL 100mg will be administered in the morning and evening on Day 6 during the Multiple-dose Period.

g PSL 200mg will be administered in the morning and evening from Day 7 to Day 9 during the Multiple-dose Period.

h PSL 200mg and 100mg will be administered in the morning and evening, respectively, on Day 10 during the Multiple-dose Period.

i PSL 100mg will be administered in the morning and evening from Day 11 to Day 12 during the Multiple-dose Period.

j Predose and 0.25, 0.5, 1, 1.5, 2, 3, 4, 6, 8, 12, 24, 36, and 48 hours postdose.

k Predose and 0.25, 0.5, 1, 1.5, 2, 3, 4, 6, 8, and 12 hours after the morning dose.

l Predose and 0 to 12 hours, 12 to 24 hours, 24 to 48 hours, 48 to 72 hours, and 72 to 96 hours postdose.

m 0 to 12 hours after the morning dose.

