## 10.4 Vital signs, Electrocardiograms, and other observations related to safety

### 10.4.1 Vital signs

The following vital sign measurements will be taken prior to blood sampling, where applicable.

- Systolic and diastolic blood pressure (mmHg)
- Pulse rate (beats per minute)
- Respiratory rate (breaths per minute)
- Body temperature (°C)

Descriptive statistics will be reported for all vital sign measurements in both standing and supine position. Observed results and changes from Baseline will be summarized by genotype group, treatment period and timepoint.

A by-participant listing of all vital sign measurements and change from Baseline will be presented by genotype group and timepoint.

The number and percentage of participants with treatment-emergent markedly abnormal (TEMA)/potentially clinically significant (PCS) vital sign values as calculated by the criteria outlined in **Table 10–2** will be summarized by vital sign variables and time point and will be presented by genotype group and overall.

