#### 10.4.2      **Electrocardiograms**

12-lead ECG will be recorded 3 times at each time point. The individual mean at each time point will be calculated as raw parameters for descriptive analysis. The individual mean and change from baseline will be summarized using descriptive statistics by treatment period, genotype and timepoint.

The following ECG parameters will be derived from digitally recorded 12-lead ECGs.

- Heart rate (HR) [beats per minute]
- RR interval [msec]
- PR interval [msec]
- QRS interval [msec]
- QT interval [msec]
- QTcF interval [msec]: QT interval corrected by Fridericia formula  $QT_cF [msec] = \frac{QT [msec]}{\sqrt[3]{RR [sec]}}$

If available in the database, the QT corrected for heart rate using Bazett's formula (QTcB) will also be included in the listings and tabulations.

The individual measurements and the mean of the triplicate measurements will be reported in the by-participant listings. The listing will also include the change from Baseline based on the mean of the triplicate measurements at each timepoint, and will be presented by treatment period, genotype group and timepoint.

Measured values and changes from Baseline will be summarized by treatment period, genotype group and timepoint (based on the mean of the triplicate values at each timepoint). Mean change

from Baseline in QTcF will be summarized by treatment period, genotype and timepoint and plotted over time by genotype. Figures will be presented with all treatment periods overlaid on the same plot by genotype.

In addition, the following cut-points in QTcF (raw data and change from Baseline) based on the mean of the triplicate data, will be summarized categorically (number and percentage of participants) by treatment period, genotype and timepoint.

For observed data:

- <450msec
- $\geq 450$  to <480msec
- $\geq 480$  to <500msec
- $\geq 500$ msec

For change from Baseline:

- <30msec
- $\geq 30$  to <60msec
- $\geq 60$ msec

All ECG findings for the individual triplicate measurements will be listed separately.

Any incomplete triplicate measurements at a given timepoint will be handled as described in Section 4.2.3.

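### Vital-sign and QTcF threshold tables count by time point only, so an off-schedule crossing is not counted and no table gives the number of participants ever affected

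*SAP*

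**What the plan says.** SAP 4.3 opens its rules in general terms: "The following general rules will apply to all repeated and unscheduled measurements". Before the first dose, the latest value is used. After it, "Unscheduled and repeated measurements will not be used in the descriptive statistics at time points after first dose of study medication". Two provisions soften this. One is that "All repeated and unscheduled measurements will be presented in the data listings, where applicable". The other concerns early withdrawal: "Unscheduled measurements performed for the Early Withdrawal (EW) visit will be assigned to the EOS visit", where they are analysed as end-of-study values.

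SAP 10.4.1 plans a table of "The number and percentage of participants with treatment-emergent markedly abnormal (TEMA)/potentially clinically significant (PCS) vital sign values", which "will be summarized by vital sign variables and time point and will be presented by genotype group and overall". SAP 10.4.2 sets QTcF cut-points for observed values and for change from Baseline, based on the triplicate mean, and these "will be summarized categorically (number and percentage of participants) by treatment period, genotype and timepoint". Neither section plans a row for any time after dosing or for the worst post-baseline value, and neither says how 4.3 applies to its counts.

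**The concern.** Leaving unscheduled readings out of means by time point is sound practice, because it keeps each mean tied to a fixed time and avoids over-weighting participants who were measured more often. A count of participants who crossed a safety limit has a different purpose. Extra readings tend to be taken because something looked or felt wrong, so they are the readings most likely to cross a limit. A table with no place for them can show zero in a group where a crossing was recorded.

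A second weakness is independent of 4.3. A participant can be abnormal at several time points, so per-time-point counts do not add up to participants affected. Even from scheduled data alone, neither table says how many participants ever crossed a limit.

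**Working it through.** The documents give no figure to reproduce, so the check is mainly textual.

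**1. Does 4.3 reach the counts?** It speaks of descriptive statistics. SAP 3.1 describes those for continuous variables and gives categorical variables frequency counts and percentages; SAP 6.1 also names the two separately. There are two readings:
- Broad: 4.3 covers the counts, and post-dose repeat and unscheduled values are excluded from them.
- Narrow: 4.3 covers continuous summaries only, and the use of repeats in the counts is not stated.

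**2. What each reading does.**

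| Situation after first dose | By-time-point threshold table |
|---|---|
| Scheduled value abnormal, recheck normal | Counted |
| Scheduled value normal, recheck abnormal | Not counted (broad); undefined (narrow) |
| Abnormal only at an unscheduled time | No row to hold it, on either reading |
| Scheduled QTcF in one category, unscheduled QTcF in a higher one | Counted in the lower category only |
| Unscheduled value taken for the early withdrawal visit | Counted as end of study |

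**3. Is there room for off-schedule crossings?** The schedule in SAP Table 2-1 is sparse: "On dosing days, vital signs will be performed predose and 3 hours postdose", and its ECG footnote names predose and 24 hours postdose. An ECG recorded during symptoms a few hours after a dose would normally be unscheduled. Protocol 8.4.3 foresees additional QTc readings, and Protocol 8 foresees repeat or unscheduled samples for safety reasons.

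**4. A case within the plan.** Protocol 7.2 makes a QTcB or QTcF of at least 500 ms, or at least 60 ms above Baseline, a withdrawal criterion, and does not require the ECG to be a scheduled one. SAP 10.4.2 has QTcF rows at the same two limits. A participant could meet the criterion by QTcF on an extra ECG while those rows show zero, unless that ECG was taken for the early withdrawal visit.

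**5. Why the counts cannot be added.** Suppose, hypothetically, that a group of 13 has a count of 1 at each of three time points. The number affected is anywhere from 1 (1/13 = 7.7%) to 3 (3/13 = 23.1%), and the table cannot say which.

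**6. Scale of one uncounted participant.** Group size is 13, and 39 in total (SAP 2.2). The intervals are exact two-sided 95%; they are for illustration, as the SAP plans none for these counts.
- 0/13 = 0%. Upper limit = 1 − 0.025^(1/13) = 24.7%.
- 1/13 = 7.7%. Lower limit = 1 − 0.975^(1/13) = 0.2%; upper limit = 0.975 quantile of Beta(2, 12) = 36.0%.
- All groups together: 0/39 = 0% becomes 1/39 = 2.6%.

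**The case against.** The best defence is that little is lost. Unscheduled values are listed. Protocol Appendix 3 makes vital-sign and ECG abnormalities judged clinically significant into adverse events, whether or not the reading was scheduled, and SAP 10.2 tabulates TEAEs by participant, period and genotype. A participant withdrawn on QTc grounds also appears in the discontinuation summaries of SAP 5.1. All of this stands. It does not close the gap, because the threshold tables apply fixed numerical limits without investigator judgment, and the adverse event tables depend on that judgment.

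It is also fair to object that pooling unscheduled ECGs may mix single tracings with triplicate means. That is a real cost, and the fix needs a rule for it.

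A reader might infer more than the documents support:
- *That 4.3 expressly bars these values from the counts.* Its wording does not settle this. The conclusion rests on the absence of a row, which holds on either reading.
- *That a normal recheck erases a scheduled abnormal value.* The post-dose rule keeps the scheduled value in the count.
- *That the overall presentation in SAP 10.4.1 means any time.* It is paired with genotype group, as in SAP 5.1, and so most naturally means all genotypes together.
- *That safety by genotype is the secondary objective.* The objective is safety and tolerability in the study participants. The SAP's secondary endpoint is TEAE incidence, with vital signs and ECG listed under other endpoints; genotype is a way of presenting the data.
- *That liver tests have the same gap.* SAP 10.3 already lists participants who reach the liver limits at any time point and summarises those who meet the criteria for potential drug-induced liver injury.

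**Conclusion.** The point holds, and it is confined to the threshold-based tables for vital signs and QTcF. A crossing found only off schedule is not counted there, a worse off-schedule value does not move a participant to the higher category, and the number of participants ever affected cannot be read from either table. One such participant changes a genotype group's entry by 7.7 percentage points. Whether any would occur, and how many, cannot be derived from the documents, so this is a possible undercount of unknown frequency. The conclusion assumes that the tables are built as written, with no rows beyond those the SAP describes. It has no bearing on the primary PK analysis or on TEAE incidence. The correction is worth making because it is cheap and these tables exist to show outliers.

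**What to change.** In SAP 4.3, state that the post-dose exclusion applies to by-time-point summaries only. In the tables of SAP 10.4.1 and 10.4.2, keep the planned rows and add one row per treatment period and genotype, labelled *any time after first dose, including unscheduled and repeat measurements*, counting each participant once per criterion or, for QTcF, in the worst category reached. Assign unscheduled readings to periods by the definitions in SAP 3.2.2. For QTcF, use the mean of the replicates available at that reading, in line with SAP 4.2.3, and footnote any count that rests on a single tracing. Means by time point stay on scheduled values, and no change is needed for liver tests.

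The cost is a few sentences in the SAP and added rows in two tables already planned. No new data are needed and the PK analysis is unchanged. Under SAP 1, a change before database lock needs an SAP amendment; after lock, the rows can be added as a supplementary analysis explained in the clinical study report.

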#### **4.4 Handling of measurements obtained at the early withdrawal visit**

Participants who withdraw early from the study for any reason, including those withdrawn from study medication, will be asked to return for the EOS Visit 7 to 7 days (+/- 1 day) after last intake of study medication and will then enter the SFU Period and will undergo the same assessments performed at the EOS Visit.

#### **4.5 Interim analyses and data monitoring**

No formal interim analyses are planned. Details about the safety analyses will be provided in the SMC Charter.

#### **4.6 Multicenter studies**

Not applicable.

#### **4.7 Multiple comparisons/multiplicity**

Not applicable.

#### **4.8 Use of an efficacy subset of participants**

Not applicable.

#### **4.9 Active-control studies intended to show equivalence**

Not applicable.

#### **4.10 Examination of subgroups**

Not applicable.

### **5 STUDY POPULATION CHARACTERISTICS**

#### **5.1 Participant disposition**

A study participant is considered to have completed the study if he has completed all periods of the study including the last scheduled procedure shown in the Schedule of activities in the protocol.

The number and percentage of participants who were enrolled into the study, participants who completed or prematurely discontinued the study, as well as the reason for discontinuation will be summarized by genotype group and overall based on the SS.

The number and percentage of participants who discontinued due to AEs will be separately summarized by genotype group and overall based on the SS.

The number and percentage of participants included into each of the analysis sets will be summarized by genotype group and overall based on the ES. Percentages will be based on the ES for this summary.

Finally, screen failure reasons will be summarized by overall, based on the ES. A listing of participants who did not meet study eligibility criteria will also be presented.

In addition, the following listings will be presented:

- Participant disposition (ES)
- Study discontinuation (SS)
- Visit dates (SS)
- Participant analysis sets (ES)

The listing of participant disposition will include the date of informed consent, date and time of first and last dose of study medication, date of premature termination and primary reason (if applicable), and primary reason (if applicable) and date of final contact.

The listing of study discontinuation will include the reason for discontinuation and the number of days on study medication.

The number of days on study medication will be calculated as follows:

$$\begin{aligned} \text{Number of days on study medication} \\ = \text{Date of last dose received} - \text{Date of first dose received} + 1 \end{aligned}$$

## 5.2 Protocol deviations

Important protocol deviations (IPDs) will be identified and classified by the deviation types in the IPD document.

Any samples that are obtained outside the tolerance window permitted at the specified timepoint will be discussed at the DEM and any possible exclusion from analysis will be documented accordingly.

A listing of all IPDs identified at the DEM will be presented by genotype group based on the SS and will include the deviation type and description. The number and percentage of participants in the SS with IPDs will be summarized by genotype group. The denominator for the percentages will be the number of participants in the SS.

